5.5.4.3 Adverse Event Evaluations

Each adverse event in the study will be evaluated by the investigator as to its severity, its relationship to the study device and to the procedure, and whether it was anticipated in the investigational plan. The distinction between an AE, an SAE, and a UADE will be made according to the definitions given above. Gynesonics is responsible for the classification of adverse events. In case of disagreements in which the investigator's evaluation is that the event is more serious and/or more related, both opinions will be included in adverse event reports.

5.5.4.3.1 Relatedness

The determination of the level of relatedness of the adverse event to the study device or procedure will be made according to the definitions below:

- 1) **Definitely Related:** The adverse event was directly and clearly related to the VizAblate device or procedure
- 2) **Probably Related:** The adverse event may have been related to the VizAblate device or procedure. Alternative causes are possible but are less likely
- 3) **Possibly Related:** The adverse event may have been related to the VizAblate device or procedure, but an alternative cause is equally likely

- 4) Unlikely to be Related: The adverse event may have been related to the VizAblate device or procedure, but an alternative cause is more likely
- 5) Definitely Not Related: The adverse event was not related to the VizAblate device or procedure

NOTE: If any adverse event is considered to be “possibly”, “probably” or “definitely” related to the use of the study device, that event will be classified as an ADE or an SADE for purposes of statistical analysis.

5.5.4.3.2 Severity of Adverse Events

Investigators will also be asked to assess the severity of all adverse events. The following definitions will be used:

- 1) Mild: Awareness of signs or symptoms, but easily tolerated; are of minor irritant type; causing no loss of time from normal activities; symptoms would not typically require medication or a medical evaluation; signs or symptoms are transient.
- 2) Moderate: Interferes with the subject’s usual activity and requires symptomatic treatment.
- 3) Severe: Symptom(s) causing severe discomfort and significant impact of the subject’s usual activity and requires treatment.

These definitions are for descriptive purposes only and are independent of the judgment of whether an event is classified as an AE or an SAE.

5.6 Statistical Methods

All statistical processing will be performed using SAS® unless otherwise stated.

Continuous variables will be summarized descriptively using number of subjects (n), mean, standard deviation (SD), minimum, median, and maximum. Categorical variables will be summarized descriptively using frequency counts and percentages.

Analyses presented for the Full Analysis Set¹ (FAS) will be considered primary. Analyses performed on the Per-Protocol (PP) will be secondary and supportive.

¹ International Conference on Harmonization (ICH) – E9 Statistical Principles for Clinical Trials

5.6.1 Analysis Populations

The FAS population will be comprised of all study subjects who were treated and who do not meet any of the following criteria:

- Become pregnant during the 12-month post-procedure study period;
- Are diagnosed with a medical condition that would make assessment of menstrual bleeding invalid or unreliable.

The safety population will be comprised of subjects who were treated and have post-baseline information.

The per-protocol (PP) population will include subjects who complete 12 months of follow-up without study protocol violations. The PP population will include subjects from the FAS population who do not meet any of the following criteria:

- Violated the inclusion/exclusion criteria;
- Did not complete a 12 month PBAC;
- Are associated with protocol violations that are considered to influence the endpoint under evaluation;

Subjects who discontinue the study due to a device/procedure-related adverse event (AE) or documented lack of efficacy (without surgical reintervention) will be included in the PP population, with missing data imputed as failure for the 12-month menstrual blood loss (MBL) endpoint.

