10.6 Subject Discontinuation or Withdrawal

- A. Subjects may be involuntarily removed from the study for failure to adhere to the protocol, failure to attend follow-up visits, or due to safety reasons. In such cases, the Investigator shall arrange for an exit visit and complete a study exit case report form for the subject.
- B. Subjects may voluntarily withdraw from the study at any time without reason. The Investigator shall make an effort to obtain an exit visit but cannot insist on the visit if the subject does not wish to come in. The Investigator shall complete a study exit case report form with as much information as is available at the time of withdrawal.
- C. In cases of early termination, as many of the month 12 study procedures should be performed as possible at the time of withdrawal. All information relative to the withdrawal must be fully documented in the subject chart.
- D. If the subject requires removal from the study due to medical reasons (i.e. adverse event) or reasons related to the procedure, the site staff should contact the Gynesonics Medical Director. Adverse device effects that are ongoing at the time of withdrawal will be reported and followed up to 6 weeks following the study treatment or until the adverse device effect resolves or is considered stable, whichever comes last, unless the subject has withdrawn consent for any such follow-up. In such cases, the final follow-up can be either a telephone contact or an office visit.
- E. A subject will be withdrawn from the study if, subsequent to enrollment, she is diagnosed with any condition that could affect menstrual bleeding volume, or if she becomes pregnant at any time following Sonata treatment. In the case of pregnancy, the Investigator and study coordinator should make every attempt to obtain basic pregnancy outcome information and complete the applicable case report form.
- F. A subject may be withdrawn after enrollment and before receiving the study treatment if, at the Investigator's discretion, she has developed a general health condition that would increase risks from study treatment

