Birth control adherence		X	X	X	X	X	X		
Sonata Treatment & Procedure Assessments Procedure & discharge times, pain VAS & tolerance, anesthesia and concomitant medications		X							
Adverse events		X	X	X	X	X	X	X	X
Concomitant medications		X	X	X	X	X	X		
ce-MRI	[Screening assessment]						X		
Return to normal daily activity**				X					
Post-procedure follow up Update to medical history and symptoms			X	X	X	X	X		
Pregnancy /pregnancy outcome				X	X	X	X	X	X
OTE and Subject satisfaction						X	X	X	X
Surgical Reintervention*						X	X	X	X

* if subject undergoes hysterectomy, operative and pathology reports shall be forwarded to study sponsor

**Subjects who are not back to normal activity will be followed weekly by phone until normal activity has resumed or is not expected to change

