5.6.4.1 Primary Efficacy Analysis

Table 3 describes the two co-primary endpoints. Each subject will be determined to be a Success or Failure per the subject success criteria. For the endpoint of Reduction in Menstrual Blood Loss, the count and percentage of subjects with Success and Failure will be summarized, along with the 95% exact confidence interval for the percent successes. The rate of surgical reintervention during 12 months, along with 95% confidence interval, will be determined using Life-Table methods. Each endpoint has a pre-specified study success criterion, as described in Table 3. Study success is achieved if both of study success criteria are met.

Table 3: Co-Primary Endpoints and Success Criteria

Co-Primary Endpoint	Test Method	Subject Success Criteria ^a	Study Success Criteria
Reduction in MBL at 12 months	Modified pictorial blood loss assessment chart (PBAC)	≥ 50% reduction in PBAC score, and a final PBAC score < 250	LCL of the percentage of subject success ≥ 45%
Rate of surgical reintervention for HMB due to treatment failure at 12 months	Surgical reintervention for HMB due to treatment failure	No surgical reintervention for HMB due to treatment failure at 12 months	LCL of the percentage of subject success ≥ 75%

^a Subject success is calculated separately for the two co-primary endpoints, such that it is possible for a subject to be considered a success for one co-primary endpoint and not for the other.

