5.6.8.2 Handling of Dropouts or Missing Data

Reduction in MBL at 12 Months

Missing 12-month menstrual blood loss data will be imputed using last observation carried forward (LOCF). Subjects which undergo surgical reintervention to manage fibroid symptoms prior to 12 months will be excluded from the Reduction in Menstrual Blood Loss analysis.

Surgical Reintervention for HMB due to Treatment Failure at 12 Months

Life-Table methods will be used to calculate the success rate and 95% confidence interval for the rate of surgical reintervention during 12 months. Therefore, subjects that are discontinued prior to 12 months for reasons other than surgical reintervention will be considered censored.

Sensitivity Analyses

Sensitivity analyses will also be conducted to examine the impact of missing data. A worst-case analysis (all missing data imputed as failures) and best-case analysis (all missing data imputed as successes) will be performed. In addition, a tipping point analysis will be performed.

Secondary Endpoint Analyses

No imputations will be made for missing secondary endpoint data.

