6. INDEX OF PLANNED END-OF-TEXT TABLES

Table 14.0.1.1: Summary of Subject Enrollment and Evaluability

Table 14.0.1.2: Summary of Subject Enrollment and Evaluability by Investigator

Table 14.0.2: Summary of Subjects Excluded from Analyses

Table 14.0.3: Summary of Subject Completion/Discontinuation

Table 14.1.1.1: Summary of Subject Demographic Characteristics (Full Analysis Set Subjects)

Table 14.1.1.2: Summary of Subject Demographic Characteristics (Safety Subjects)

Table 14.1.1.3: Summary of Subject Demographic Characteristics (Per-Protocol Subjects)

Table 14.1.2.1: Summary of Subject Baseline Characteristics (Full Analysis Set Subjects)

Table 14.1.2.2: Summary of Subject Baseline Characteristics (Safety Subjects)

Table 14.1.2.3: Summary of Subject Baseline Characteristics (Per-Protocol Subjects)

Table 14.2.1.1: Summary of Efficacy by Evaluation – Primary Efficacy Variables (Full Analysis Set Subjects)

Table 14.2.1.2: Summary of Efficacy by Evaluation – Primary Efficacy Variables (Per-Protocol Subjects)

Table 14.2.2.1: Summary of Efficacy by Evaluation – Secondary Efficacy Variables (Full Analysis Set Subjects)

Table 14.2.2.2: Summary of Efficacy by Evaluation – Secondary Efficacy Variables (Per-Protocol Subjects)

Table 14.2.3.1.1: Pooling Analysis of the Co-Primary Efficacy Endpoints (Full Analysis Set Subjects)

Table 14.2.3.1.2: Summary of Co-Primary Efficacy Endpoints by Analysis Center (Full Analysis Set Subjects)

Table 14.2.3.2.1: Analysis of Co-Primary Efficacy Endpoints (Full Analysis Set Subjects)

Table 14.2.3.2.2: Analysis of Co-Primary Efficacy Endpoints (Per-Protocol Subjects)

Table 14.2.3.2.3: Sensitivity Analysis of Co-Primary Efficacy Endpoints (Full Analysis Set Subjects)

Table 14.2.3.3.1: Summary of Secondary Efficacy Endpoints (Full Analysis Set Subjects)

Table 14.2.3.3.2: Summary of Secondary Efficacy Endpoints (Per-Protocol Subjects)

Table 14.2.3.4: Summary of Co-Primary Efficacy Endpoints by Subgroups (Full Analysis Set Subjects)

Table 14.2.4: Summary of Procedure Information (Full Analysis Set Subjects)

Table 14.3.1.1.1: Summary of Treatment-Emergent Adverse Events (TEAEs) that Resulted in Discontinuation from the Study (Safety Subjects)

Table 14.3.1.2.1: Summary of Treatment-Emergent Adverse Event Characteristics by Time Period (Safety Subjects)

Table 14.3.1.2.2: Summary of Subjects Reporting Treatment-Emergent Adverse Events (TEAEs) by Time Period (Safety Subjects)

CONFIDENTIAL

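### The diagnosis exclusion in the primary FAS also applies to the surgical-reintervention co-primary, where it can delete a recorded failure; the case is narrow and the fix is cheap.

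*SAP*

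**What the plan says.** SAP 5.6.1 builds the FAS from all treated women and then removes two groups: those who become pregnant within 12 months of the procedure, and those who "Are diagnosed with a medical condition that would make assessment of menstrual bleeding invalid or unreliable". The pregnancy criterion has a time window. The diagnosis criterion has none, names no endpoint, and makes no exception for a reintervention that came first.

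This set carries the primary analysis of both co-primaries. SAP 5.6 makes FAS results primary and per-protocol results supportive. In SAP section 6, Table 14.2.3.2.1 puts both co-primaries on the FAS, and Table 14.2.3.2.3 is titled "Sensitivity Analysis of Co-Primary Efficacy Endpoints (Full Analysis Set Subjects". The per-protocol set gives no second look, because "The PP population will include subjects from the FAS population".

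Two other rules touch the same women:

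- SAP 5.6.8.2, for the reintervention life table: "subjects that are discontinued prior to 12 months for reasons other than surgical reintervention will be considered censored".
- Protocol 10.6 E withdraws a woman if, after enrollment, "she is diagnosed with any condition that could affect menstrual bleeding volume".

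Subject success on the second co-primary (SAP Table 3) is "No surgical reintervention for HMB due to treatment failure at 12 months". SAP 5.6.2 and Table 14.0.2 report exclusions with reasons.

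**The concern.** The stated ground for the exclusion is that bleeding can no longer be assessed reliably. That is a reason to leave the menstrual blood loss (MBL) analysis. It is a weaker reason to leave the reintervention analysis, where the outcome is a listed procedure with a recorded date (SAP 5.5.1.2; Protocol 12.3), observed up to withdrawal whether or not the bleeding chart can be interpreted.

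What is at stake is a recorded failure. Suppose a woman has a reintervention for heavy bleeding due to treatment failure and is then given such a diagnosis. As written, she leaves the FAS with her event. She is then absent from the life table, from the worst-case, best-case and tipping-point analyses, and from the per-protocol set. SAP 5.6.8.2 already takes women reintervened on for fibroid symptoms before 12 months out of the MBL analysis, so her failure would appear in neither co-primary. The safety tables need not show it either, because an elective reintervention for heavy bleeding is not an adverse event (SAP 5.5.4.2, Note 3).

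**Working it through.** **1. How the rules act on each woman**

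| Woman | SAP 5.6.1 | SAP 5.6.8.2, if she were in the set |
|---|---|---|
| Qualifying reintervention, then a diagnosis that makes bleeding assessment invalid or unreliable | Removed with her event | Event |
| Same diagnosis, no event | Removed with her time at risk | Censored |
| Condition that could affect bleeding volume but does not make its assessment invalid or unreliable (withdrawn under Protocol 10.6 E only) | Stays | Censored if event-free |

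Only the first row loses a failure. The second matters little. With 15 events in 147 women, censoring 5 event-free women in a single actuarial interval gives 1 − 15/(147 − 2.5) = 89.6%. Deleting them gives 1 − 15/142 = 89.4%.

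**2. The plan's own figure**

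Inputs: lower 95% limit ≥ 75%, assumed success 90%, N = 75 for 90% power (SAP Table 4). With two-sided exact (Clopper-Pearson) limits, 75 women need at least 64 successes. Power at 90% is 93.1% and the one-sided error at 75% is 2.2%. The stated N is reproduced.

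**3. One deletion near the threshold**

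N = 147 treated (Protocol 19.1 C). The exact limit stands in for the life-table limit, with no other censoring.

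- 121/147 = 82.3%, lower limit 75.17%: passes.
- 120/147 = 81.6%, lower limit 74.41%: fails.
- Remove one of the 27 reintervened women: 120/146 = 82.2%, lower limit 75.006%: passes.

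At the planned rate, 15 events in 147 give 89.8% (limit 83.7%). Removing 3 of those events gives 132/144 = 91.7% (limit 85.9%). The criterion is met either way.

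**4. Chance of passing under assumed removal**

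The documents give no removal rate, so all rates here are assumptions. Let f ~ Bin(147, 1 − p) be reintervened women, kf ~ Bin(f, qf) those removed, and ks ~ Bin(147 − f, qs) the event-free women removed. The trial passes if 147 − f − ks reaches the exact critical count for 147 − kf − ks women.

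| Removed: reintervened v other | True 75% | True 90% |
|---|---|---|
| 0 v 0 | 2.2% | 99.9% |
| 5% v 5% | 1.9% | 99.7% |
| 5% v 2.5% | 2.7% | 99.8% |
| 10% v 5% | 3.6% | 99.9% |
| 5% v 0 (bound) | 3.8% | 99.9% |
| 10% v 0 (bound) | 6.2% | >99.9% |
| 2.5% v 5% (reverse) | 1.4% | 99.6% |

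**5. Check on the stand-in**

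A simulated life table (12 monthly actuarial intervals, exponential event times, 15% uniform dropout, log-log Greenwood limits) gives 1.9% with no removal at a true 75%, 2.5% for 5% v 2.5%, and 5.7% for 10% v 0. The pattern is the same. Plain Greenwood limits give 3.6% with no removal; that excess comes from the interval method, not from the FAS.

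**The case against.** Four arguments on the other side have force.

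First, a reader might infer that SAP 5.6.1 and 5.6.8.2 contradict each other and leave the analyst to choose. The documents do not support that. The first defines who is analysed and the second handles missing data among those analysed, so on the ordinary reading the exclusion governs. Nor do Protocol 10.6 E and SAP 5.6.1 set the same test: withdrawal needs only a condition that might affect volume, while exclusion needs one that defeats assessment.

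Second, the harmful case needs two things in one woman. A diagnosis that explains her bleeding may mean that the surgery was not due to treatment failure, and then it counts against the device in no set. Screening also excludes adenomyosis, endometriosis, hyperplasia, coagulopathy and recent pelvic malignancy, which limits new diagnoses.

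Third, a reader might infer that operated women will be diagnosed more often, because "if subject undergoes hysterectomy, operative and pathology reports shall be forwarded to study sponsor". That is plausible but not stated. The FSH work-up for amenorrhea can yield diagnoses in women who were never operated on. Equal or reverse imbalance lowers the chance of passing.

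Fourth, exclusions are reported with reasons, so removals will be visible.

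All four stand as limits on size and likelihood. None restores a deleted event: the listing counts exclusions without analysing their effect, and the planned sensitivity analyses never include these women.

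**Conclusion.** The point holds in narrow form. An exclusion justified by bleeding measurement also applies to a co-primary that does not use the bleeding chart, and followed as written it can delete a recorded qualifying reintervention from every planned analysis of that endpoint.

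The effect is small and conditional. It needs diagnoses to fall more often on reintervened women, at rates the documents do not give. With 5% v 2.5% removal, the chance of passing at a true 75% moves from 2.2% to 2.7%, close to the nominal 2.5%. The 6.2% figure is a bound with no event-free woman removed. The one-deletion reversal needs exactly 27 events and clears 75% by 0.006 percentage points. At the planned 90% success, passing is all but certain under every pattern tried.

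A claim that the exclusion inflates the reintervention result, or biases MBL in a known direction, goes beyond the documents. This is a cheap improvement of low impact.

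**What to change.** In SAP 5.6.1 and 5.6.8.2:

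1. Define the reintervention analysis set as all treated women. Count as an event any reintervention for heavy menstrual bleeding due to treatment failure that is observed before censoring. Otherwise censor at withdrawal, including withdrawal for diagnosis or pregnancy, in the life table already planned.
2. Confine the diagnosis and pregnancy exclusions to the MBL analysis, which is otherwise unchanged.
3. State how the withdrawal test in Protocol 10.6 E relates to the exclusion test in SAP 5.6.1.
4. Run the planned worst-case sensitivity analysis for reintervention on this all-treated set as well, because censoring at a bleeding-related diagnosis may be informative.

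Cost: SAP wording and one rerun of an analysis already planned. Sample size and data collection do not change. The reintervention-free rate may come out slightly lower. If the sponsor chose to edit the protocol as well, the amendment rules in Protocol 16.2 would apply. How surgery is judged to be due to treatment failure is a separate question that this change does not settle.

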5.5.1.2 Surgical Reintervention

Subjects will be asked to indicate whether there has been any surgical reintervention for the treatment of HMB since their last visit. The rate of surgical reintervention for HMB due to treatment failure will be evaluated throughout all assessment timepoints and at 12 months as a co-primary endpoint. Surgical reintervention for the treatment of HMB includes the following procedures:

- a) Hysterectomy (abdominal, vaginal, laparoscopic)
- b) Myomectomy (abdominal, vaginal, laparoscopic, hysteroscopic)
- c) Uterine artery embolization
- d) Magnetic resonance-guided focused ultrasound (MRgFUS) or similar focused ultrasound treatment
- e) Endometrial ablation (nonresectoscopic, hysteroscopic)

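### The single per-protocol set requires a 12-month PBAC for both co-primaries, so it can drop reintervention events from the supportive reintervention analysis and tends to bias that rate upward

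*SAP*

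**What the plan says.** SAP 5.6 makes the FAS primary and says of the other set: "Analyses performed on the Per-Protocol (PP) will be secondary and supportive".

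SAP 5.6.1 defines a single PP population. It opens with a general condition: "The per-protocol (PP) population will include subjects who complete 12 months of follow-up without study protocol violations". It then lists three grounds for removing FAS women:

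- a breach of the eligibility criteria;
- "Did not complete a 12 month PBAC";
- "Are associated with protocol violations that are considered to influence the endpoint under evaluation".

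Only the third ground is tied to an endpoint. A closing paragraph readmits two kinds of early leaver, counted as failures for menstrual blood loss (MBL) if that value is missing. One is women who leave because of a device- or procedure-related adverse event. The other is women with "documented lack of efficacy (without surgical reintervention) will be included in the PP population".

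The index in SAP 6 applies this one set to both co-primaries: "Table 14.2.3.2.2: Analysis of Co-Primary Efficacy Endpoints (Per-Protocol Subjects".

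The reinterventions listed in SAP 5.5.1.2 begin with "Hysterectomy (abdominal, vaginal, laparoscopic"; the other four categories are myomectomy, uterine artery embolization, focused ultrasound and endometrial ablation. SAP 5.6.8.2 excludes reintervened women from the MBL analysis only. For the reintervention endpoint it plans a life-table, with censoring for discontinuation for other reasons.

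**The concern.** For MBL, requiring a 12-month chart is a natural per-protocol condition. For reintervention it is not, because the event itself can be the reason why the chart is missing. After a hysterectomy there is no menstrual cycle to record, and neither document assigns such a woman a score or exempts her from the criterion. The condition of 12 completed months works in the same direction for a woman who leaves after her reintervention.

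Followed as written, the rule can remove some of the failures that the PP reintervention analysis is meant to count. A supportive analysis is useful because it can contradict the primary one. Here the PP table could show the 75% criterion met beside an FAS result that misses it, and nothing in that table would tell the reader why.

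**Working it through.** **Who is removed.** Consider a woman with a qualifying reintervention before month 12.

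| Her course | 12-month PBAC? | Readmitted? | Counted as a PP event? |
|---|---|---|---|
| Stays, still menstruates, returns the chart | Yes | Not needed | Yes |
| Hysterectomy, no chart | No | No | No |
| Leaves after the reintervention, no chart | No | No, if she leaves for lack of efficacy | No |
| Leaves because of a device- or procedure-related adverse event | No | Yes, reading the reintervention limit as attached to lack of efficacy only | Yes |

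The loss is therefore partial, and its extent depends on how many reintervened women lack the chart.

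**Inputs.** Lower-limit criterion 75%, assumed success 90%, N = 75 (protocol 19.1 B, SAP Table 4). N = 125 from the MBL calculation (protocol 19.1 A, SAP Table 4). The share of reintervened women without a 12-month PBAC is not in the documents, so it runs from none to all.

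**Plan's own figures.** With x successes in n, the exact two-sided 95% lower limit L is the 0.025 quantile of a Beta(x, n − x + 1) distribution.

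- Reintervention, n = 75: the criterion is met from x = 64. P(X ≥ 64 | 0.90) = 0.931.
- MBL, n = 125: the 45% criterion is met from x = 68. P(X ≥ 68 | 0.60) = 0.914.

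Both agree with the stated 90% power.

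**Effect on the PP rate.** Let e be the number of events among N = 125 and d the number dropped for want of a chart. With no other exclusions, dropped events leave the denominator and the successes are untouched:

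PP rate = (125 − e) / (125 − d).

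| Events e | Dropped d | PP rate | Exact lower limit | 75% criterion |
|---|---|---|---|---|
| 25 | 0 | 100/125 = 80.0% | 71.9% | Fails |
| 25 | 5 | 100/120 = 83.3% | 75.4% | Passes |
| 25 | 13 | 100/112 = 89.3% | 82.0% | Passes |
| 25 | 25 | 100/100 = 100% | 96.4% | Passes |
| 13 | 0 | 112/125 = 89.6% | 82.9% | Passes |
| 13 | 7 | 112/118 = 94.9% | 89.3% | Passes |
| 13 | 13 | 112/112 = 100% | 96.8% | Passes |

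The rows with d = 0 are also the full-set results. Thirteen events is close to the planned 90% success. With 25 events, 5 dropped is the turning point: with 4 dropped, 100/121 = 82.6% has a lower limit of 74.7% and still fails.

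These are simple proportions with exact limits. The SAP specifies a life-table with censoring, so the figures show direction and order of size, not what the planned analysis would print.

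**The case against.** **No decision rests on this.** That stands. The FAS is primary, and its life-table counts reinterventions as events. Worst-case, best-case and tipping-point analyses are planned on the FAS (SAP 5.6.8.2; Table 14.2.3.2.3). SAP 5.6.2 also has the reasons for exclusion from each population summarized, so an attentive reader could find the lost events.

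**A reader might infer that the PP analysis can never contradict a favourable FAS result.** The documents do not support that. The PP criteria also remove event-free women, which pulls the rate down. Take an FAS result of 105/125 = 84.0% (lower limit 76.4%, a pass). If the PP set drops 19 event-free women (about 15% of 125, the dropout assumed in protocol 19.1 C) and 3 of the 20 events, it has 105 − 19 = 86 successes among 125 − 22 = 103 women. That is 83.5% (lower limit 74.9%, a fail). The bias from dropped events is upward, but the net movement can go either way.

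**A reader might also infer that only women who chart a cycle at month 12 can count as events, or that the rate is driven to 100%.** Neither follows. The adverse-event route readmits some women, and four of the five listed procedure categories are not hysterectomy. No section withdraws a woman because of a reintervention. Protocol 10.6 C asks for as many month-12 procedures as possible at early termination, though it does not say whether such a chart counts as the 12-month PBAC. A site might also record a zero chart after hysterectomy. The share dropped could be small, and at zero there is no effect.

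None of this answers the text. The PBAC criterion is not limited to MBL, and the lack-of-efficacy route leaves reintervened women out.

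**Conclusion.** The point holds for the supportive PP analysis of reintervention. As written, SAP 5.6.1 makes membership for that endpoint depend partly on the outcome, so the PP reintervention-free rate tends to be biased upward. This comes from a stated rule, not from missing detail. The FAS analysis and the study success decision are untouched.

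The size depends on a share that the documents do not give. In the illustration, a full-set result that misses the criterion at 80.0% becomes a PP pass once 5 of 25 events (20%) are dropped. Near the planned rate, 89.6% rises to 94.9% with 7 of 13 events dropped and to 100% only if all are. This assumes N = 125, no other exclusions, and simple proportions in place of the life-table.

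It should be corrected before the analysis, but it does not threaten the primary conclusion.

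**What to change.** In SAP 5.6.1, define the PP set by endpoint.

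- **MBL.** Keep the 12-month PBAC criterion, the requirement to complete 12 months of follow-up, and the existing readmission paragraph. State that all three apply to this endpoint only. Amending the PBAC bullet alone would not be enough, because the opening sentence separately excludes reintervened women who leave.
- **Reintervention.** Include every FAS woman who meets the eligibility and protocol-violation criteria, applied identically to women with and without an event. Keeping all reintervened women regardless of compliance would make membership outcome-dependent in the other direction. Count a qualifying reintervention by month 12 as an event whether or not there is a PBAC. Censor other early leavers by the life-table method already planned in SAP 5.6.8.2.

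The cost is a change of SAP wording and one extra population flag, with no new data. The PP reintervention-free rate may become less favourable.
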